8.2.5. Height, Weight and Physical Examination

Height (in cm) and weight (in kg) will be measured at all study visits. A full physical

examination (including evaluation of the cardiovascular system, chest and lungs, thyroid, abdomen, nervous system, skin and mucosae, musculoskeletal system, eyes, ears, nose, mouth, throat, spine, lymph nodes, and extremities) will be conducted at Screening (Visit 1) and 4-week Follow-up (Visit 8), 4 weeks after discontinuation of study drug.

Physical examinations may also be performed at any time during the study as clinically indicated.

8.2.6. Confirmatory Gene Sequencing

A blood sample for dystrophin gene sequencing will be drawn at Screening (Visit 1). The study manual should be referenced for collection, processing, and shipping information.

8.2.7. Central Laboratory Assessments

All laboratory samples will be analyzed by a central laboratory. Please refer to the study manual for instructions regarding collection, processing, and shipment of all laboratory samples.

8.2.7.1. Hematology Laboratory Assessment

Hematology laboratory assessments will include white blood cell count with differential, hemoglobin, hematocrit, other red cell parameters, and platelet count. These parameters will be measured at every protocol-specified study visit. The study manual should be referenced for collection, processing, and shipping information.

8.2.7.2. Biochemistry Laboratory Assessment

Biochemistry laboratory assessments will include sodium, potassium, chloride, bicarbonate, blood urea nitrogen, creatinine, magnesium, calcium, phosphorus, uric acid, glucose, total protein, albumin, bilirubin (total, direct, and indirect), AST, ALT, GGT, CK, lactate dehydrogenase, alkaline phosphatase, total cholesterol, high-density lipoprotein, low-density lipoprotein, triglycerides, and cystatin C. These parameters will be measured at every protocol-specified study visit. The study manual should be referenced for collection, processing, and shipping information.

8.2.7.3. Urinalysis

Urinalysis will include analysis for pH, specific gravity, glucose, ketones, blood, protein, urobilinogen, bilirubin, nitrite, and leukocyte esterase. These parameters will be measured at every protocol-specified study visit. The study manual should be referenced for collection, processing, and shipping information.

8.2.8. 12-Lead ECG

A 12-lead ECG will be obtained at screening, Week 4 (Visit 3), Week 52 (Visit 7/ET), and 4-week Follow-up (Visit 8). ECGs will be read locally at investigational sites and interpreted for clinical significance. The findings will be captured in source documents and within the eCRF.

8.2.9. Timed Function Tests

Timed function tests will include the time taken to run/walk 10 meters, time to climb 4 stairs, time to descend 4 stairs, and time to stand up from a supine position [[Mendell 1989](#), [Griggs 1991](#), [Beenakker 2005a](#), [Pradhan 2006](#)] (see Study Manual for detailed instructions). These parameters will be assessed prior to ataluren dosing on the first day of treatment (Visit 2), Week 28 (Visit 5), and Week 52 (Visit 7/ET).

8.2.10. North Star Ambulatory Assessment

The NSAA will be used to evaluate physical function, using standardized procedures (see Study Manual for detailed instructions). The NSAA will be performed prior to ataluren dosing on the first day of treatment (Visit 2), Week 28 (Visit 5), and Week 52 (Visit 7/ET).

8.2.11. Pharmacokinetic Assessment

During PK assessment on Days 1 and 28, patients will remain in the clinic until all blood draws are complete. On Days 1 and 28, blood samples for PK assessment will be drawn pre-dose and 1 (± 15 min), 2 (± 15 min), 4 (± 30 min), 6 (± 30 min), 8 (± 30 min), and 10 (± 30 min) hours post-dose. These samples will be sent to a central bioanalytical laboratory for analysis of ataluren levels. Please refer to the study manual for instructions regarding the collection, processing and shipment of all PK samples to the bioanalytical laboratory.

8.2.12. Palatability Questionnaire

The palatability questionnaire assessing characteristics of the study drug such as smell and taste will be administered at Week 4 (Visit 3). A parent/caregiver may respond on the patient's behalf after discussing each item with the patient, age permitting.

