8. SCHEDULE OF EVENTS AND STUDY PARAMETERS

8.1. Schedule of Events

The types and timing of data to be recorded are summarized in Table 2. Please see [Section 8.2](#) for explanations of the study procedures outlined.

Table 2: Schedule of Events

	Screening	Ataluren Treatment						4-Week Follow-Up
Day (± 2)	-28	1 ^a	28	112	196	280	364	392
Weeks	-4	0	4	16	28	40	52/ET ^b	56
Visit	1	2	3	4	5	6	7	8
Informed consent	X							
Clinical and medication history	X							
Vital signs	X	X	X	X	X	X	X	X
Height	X	X	X	X	X	X	X	X
Weight	X	X	X	X	X	X	X	X
Physical examination	X	As clinically indicated						X
Hematology	X	X	X	X	X	X	X	X
Blood sample for gene sequencing ^c	X							
Biochemistry ^d	X	X	X	X	X	X	X	X
Urinalysis	X	X	X	X	X	X	X	X
12-lead ECG	X		X				X	X
Timed function tests		X			X		X	
North Star Ambulatory Assessment		X			X		X	
Blood for ataluren PK ^e		X	X					
Palatability questionnaire			X					
Drug administration		X-----X						
Adverse events		X-----X						X
Concomitant medications	X							X
Non-DMD-related adverse events								X

^a All study and laboratory assessments on the first day of treatment must be done prior to ataluren dosing.

^b Patients who terminate the study early should complete all assessments required for Week 52/ET (Visit 7) and will be required to return 4 weeks from the final dose of study medication for the 4-Week Follow-up Visit.

^c Verification that a blood sample has been drawn for sequencing of the dystrophin gene. A patient who has written documentation of a nonsense mutation as the cause of DMD need not wait for confirmatory results to start study drug as long as the confirmatory blood sample for gene sequencing was drawn.

^d Biochemistry laboratory assessments will include hepatic transaminases and additional parameters as specified in Section 8.2.7.2.

^e On Days 1 and 28, blood samples for PK assessment will be drawn pre-dose and 1 (± 15 min), 2 (± 15 min), 4 (± 30 min), 6 (± 30 min), 8 (± 30 min), and 10 (± 30 min) hours post-dose.

Abbreviations: ECG = electrocardiogram, ET = early termination, PK = pharmacokinetics

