8.2.1.3. End of Treatment

If the patient discontinues treatment prematurely, the procedures required for Week 52 (Visit 7/ET) should be performed before the patient leaves the study and the patient should return for the 4-Week Post-Treatment Follow-up Visit.

Please refer to [Section 10](#) for further details regarding patient withdrawal procedures.

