10. WITHDRAWAL OF SUBJECTS

All patients who receive ataluren should remain in the study whenever possible. However:

- The parent/caregiver has the right to withdraw consent and discontinue ataluren at any time.
- If the patient's condition substantially worsens after initiating ataluren, the patient will be carefully evaluated by the Investigator. The patient will be withdrawn from treatment if continuing would place them at risk.
- The Investigator may withdraw the patient from ataluren, if, in the Investigator's clinical judgment, it is not in the patient's best interest to continue.
- In the event that the patient becomes significantly noncompliant with ataluren administration, study procedures, or study requirements, the patient should be withdrawn from ataluren when the circumstances surrounding noncompliance increase risk to the patient or are anticipated to substantially compromise the interpretation of study results.
- This study may be discontinued by the relevant regulatory authority, IRB/EC, and/or PTC Therapeutics at any time.

The date ataluren is discontinued and the reason for discontinuation will be recorded in the source documents and in the eCRF. The PTC medical monitor (or designee) should be informed via e-mail of when a patient discontinues study drug.

When ataluren is discontinued (regardless of the reason), the Investigator is expected to capture all of the evaluations required at the end of treatment or Follow-up and any additional evaluations should be completed that may be necessary to ensure that the patient is free of untoward effects. The patient should be encouraged to seek appropriate follow-up for any continuing health problems.

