The total of the previous 17 items will be summed on an intra-subject basis to obtain the total score. The best total score is 34 and the worst is 0.

Recent updates to the NSAA have removed ‘Lifts Head’ from the total score. Although the results from all 17 items have been collected, a summary will be presented based on the 16 items without the result from ‘Lifts Head’. The results of these 16 items will be summed on an intra-subject basis to obtain the total score. The best total score is 32 and the worst is 0.

Two additional subset summaries will be generated from the 17 items in the NSAA. The first is an 8-item NSAA subscale. This 8-item subscale will include the following 8 items from the full NSAA.

- Stand (0, 1 or 2)
- Walk (0, 1 or 2)
- Stand up from chair (0, 1 or 2)
- Climb box step – right (0, 1 or 2)
- Climb box step – left (0, 1 or 2)
- Gets to sitting (0, 1 or 2)
- Jump (0, 1 or 2)
- Run (10m) (0, 1 or 2)

The total of these 8 items will be summed on an intra-subject basis to obtain the total score for the 8-item subscale. The best total score is 16 and the worst is 0.

The second is a 3-item NSAA subscale. This 3-item subscale will include the following 3 items from the full NSAA.

- Stand (0, 1 or 2)
- Walk (0, 1 or 2)
- Stand up from chair (0, 1 or 2)

The total of these 3 items will be summed on an intra-subject basis to obtain the total score for the 3-item subscale. The best total score is 6 and the worst is 0.

Two additional measures will also be recorded and summarized.

- Rise from Floor Time (seconds)
- Run (10m) Time (seconds)

Ataluren palatability characteristics will be based on the parent/caregiver questionnaire. The first question below will be asked of the subject and the response from the subjects will be recorded as *bad, not sure, or good*. The second and third questions will be asked of the caregiver and the response from the caregiver will be recorded as *strongly disagree, disagree, neither agree nor disagree, agree, or strongly agree*. The specific questions are presented below.

- *How did the medicine taste?*
- *On the basis of reaction/facial expression of your child, do you think that the medication is pleasant?*
- *You sometimes have problems in giving the medication to your child because he/she refuses to take it or throws it up.*

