4. ANALYSIS POPULATIONS

All subjects who receive at least 1 dose of ataluren will be included in the analyses of safety. The results from this study will be presented using 4 populations:

Enrolled Subjects: All subjects who were successfully screened and enrolled into the study.

Safety Population: All subjects who receive at least 1 dose of ataluren. The safety population will be used for the safety summary.

PK Population: All subjects who receive at least 1 dose of ataluren and have at least 1 PK concentration data. The PK population will be used for PK analyses.

Evaluable Population: All subjects who receive at least 1 dose of ataluren and have baseline and at least 1 post-baseline measurement for TFTs, NSAA, or response to the *palatability of ataluren* questions. The evaluable population will be used for the efficacy analyses.

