- All mean and median values will be formatted to one more decimal place than the measured value. SD values will be formatted to 2 more decimal places than the measured value. Minimum and maximum values will be presented with the same number of decimal places as the measured value.

- The number and percentage of responses will be presented in the form XX (XX.X%).
- Although the primary interest will be descriptive for summarizing the results from this study, there may be interest in calculating probability values for certain parameters for informational purposes. If presented, probability values will be rounded to 4 decimal places. All probability values that round to 0.0000 will be presented as '<0.0001' and p-values that round to 1.0000 will be presented as '>0.9999'. Probability values <0.05 will be considered statistically significant.
- All summary tables will include the analysis population sample size (i.e., number of subjects).
- Study Day 1 is defined as the day the subject is exposed to the study drug. All *study days* are determined relative to the day of exposure to the study drug (active or placebo).
- Baseline values will be defined as those values recorded closest to, but prior to, the first study treatment on Day 1.
- Change from baseline will be calculated as follows:

$$\text{Change} = \text{Post-baseline value} - \text{baseline value}$$

- Missing data may have an impact upon the interpretation of the trial data. However, as this study is of short duration, it is anticipated that missing data will be minimal. Missing data will not be imputed; however, a methodology is defined for missing and partial dates (see Section 9.1.3). In the event of a missing laboratory test result, the result will be treated as missing for the laboratory abnormality summary.
- Date variables will be formatted as DDMMYY for presentation.
- Tables, figures, and listings will be presented in landscape orientation.
- SAS® Version 9.3 or higher will be the statistical software package used for all data analyses.
- The subject number will be included in all data listings. All listings will be sorted by subject number and visit date, as applicable.

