10.3. Palatability Characteristics

The responses to the Ataluren Palatability Questionnaire will be summarized in Table 14.2.3 entitled *Summary of the Palatability Characteristics at Visit 3* for all subjects in the Evaluable Population. The Ataluren Palatability Questionnaire has three questions, one for the child and two for the parent/caregiver. The questions, along with the response choices are:

1. Child: How did the medicine taste?
Responses: Bad, Not Sure, Good

2. Parent / Caregiver: On the basis of reaction / facial expression of your child, do you think that the medication is pleasant?
Responses: Strongly Disagree, Disagree, Neither Agree nor Disagree, Agree, Strongly Agree

3. Parent / Caregiver: You sometimes have problems in giving the medication to your child because he/she refuses to take it or throws it up.
Responses: Strongly Disagree, Disagree, Neither Agree nor Disagree, Agree, Strongly Agree

The counts and percentages for each question and response will be summarized at Visit 3. The supportive listing will be Listing 16.2.6.3 entitled *Palatability Characteristics*. This listing will be sorted by subject number and question.

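### Palatability is asked only at Week 4 and not at early termination, so a boy who stops sooner through refusal or vomiting would give no answer and the unfavourable share could be understated

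*Protocol*

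**What the plan says.** Palatability is the last of five secondary objectives (Protocol Section 3.2) and a secondary endpoint (Section 3.4).

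- **When it is asked.** Protocol Section 8.2.12: "The palatability questionnaire assessing characteristics of the study drug such as smell and taste will be administered at Week 4 (Visit 3"). Table 2 has a single mark for it, at Day 28, and the schedule in SAP Section 16 agrees.
- **What an early stopper completes.** Table 2, footnote b: "Patients who terminate the study early should complete all assessments required for Week 52/ET (Visit 7"). Protocol Section 8.2.1.3 likewise says that "the procedures required for Week 52 (Visit 7/ET) should be performed before the patient leaves the study", followed by the 4-week follow-up visit. Neither visit includes the palatability form.
- **What is asked.** The form has three items. The child rates the taste; the caregiver judges whether the medicine seems pleasant, and then rates agreement with "You sometimes have problems in giving the medication to your child because he/she refuses to take it or throws it up" (SAP Section 3.4.2).
- **How it is summarised.** SAP Section 10.3: "The counts and percentages for each question and response will be summarized at Visit 3", for the Evaluable Population, in Table 14.2.3. SAP Section 5: "Missing data will not be imputed".
- **Who is in the analysis set.** SAP Section 4 admits treated boys who "have baseline and at least 1 post-baseline measurement for TFTs, NSAA, or response to the" palatability questions. Baseline and ET function tests are therefore enough to qualify a boy who never answered a palatability question.

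**The concern.** The third item asks about refusing the drug or throwing it up. The same behaviour can end treatment. Protocol Section 10 lets a parent stop at any time, and its clause beginning "In the event that the patient becomes significantly noncompliant with ataluren administration" provides for withdrawal from ataluren when the noncompliance adds risk or would undermine interpretation. Persistent refusal or vomiting in the first four weeks could thus produce both an unfavourable opinion and its absence from the data. Missingness of that kind depends on the outcome, and a Visit 3 summary of responders cannot correct for it.

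What is at stake is the description of one secondary endpoint in boys aged 2 to under 5. With 12 planned boys, each one carries 1/12 = 8.3 percentage points.

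**Working it through.** The documents state no palatability figure, so there is none to reproduce. The check has two parts.

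**1. Is there any route by which an early stopper's answer is obtained?** A boy who stops after Visit 3 has already answered, so the gap is confined to about the first 28 days. A boy who stops before Visit 3 has the ET visit and the follow-up visit. Neither schedule marks the form at either visit, SAP Section 10.3 draws on Visit 3 only, and nothing is imputed. There is no route.

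**2. How much could it matter?**

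Inputs:
- N = 12 (Protocol Section 11.1; Section 5.1 says at least 12).
- k = boys stopping before Visit 3 for refusal or vomiting. Assumed, 1 to 3.
- u = unfavourable answers among the 12 − k responders to an item. Assumed; 2 is used below.
- Every early stopper is counted as unfavourable. This is a worst case.

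Formulas:
- Reported share, responder denominator: u/(12 − k)
- Reported share, Evaluable N, if the stoppers qualify through ET function tests: u/12
- Share with the stoppers included: (u + k)/12

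| k | u/(12 − k) | u/12 | (u + k)/12 |
|---|---|---|---|
| 1 | 2/11 = 18.2% | 2/12 = 16.7% | 3/12 = 25.0% |
| 2 | 2/10 = 20.0% | 2/12 = 16.7% | 4/12 = 33.3% |
| 3 | 2/9 = 22.2% | 2/12 = 16.7% | 5/12 = 41.7% |

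On the Evaluable N the shortfall is k/12, or 8.3 points per stopper. On responders it is (u + k)/12 − u/(12 − k) = k(12 − k − u)/[12(12 − k)]. For k = 1 and u = 2 this is 9/132 = 6.8 points.

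The favourable share depends on the denominator. Suppose that k = 1 and the 9 other responders are all favourable. The responder basis then gives 9/11 = 81.8%, against 9/12 = 75.0% with the stopper included. The Evaluable N gives 9/12 = 75.0% either way, so the favourable share is not inflated there.

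If the single stopper would not have been unfavourable on a given item, the full-sample share is 2/12 = 16.7% and nothing is understated. For k = 1 and u = 2 the full-sample value therefore lies between 16.7% and 25.0%.

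**How likely is at least one such stop?** The documents give no rate. With an assumed per-boy risk p, the chance among 12 is 1 − (1 − p)^12:

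| p | 2% | 5% | 10% | 20% |
|---|---|---|---|---|
| Chance of at least one | 21.5% | 46.0% | 71.8% | 93.1% |

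**The case against.** Four things can be said for the plan.

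**The bias is not established.** A reader might infer that the palatability result is biased favourably as a matter of fact. The documents do not support that. The window is about four weeks, Protocol Section 10 wants patients kept in the study where possible, and SAP Section 5 expects few missing data. Vomiting is among the events listed for the three patients under 6 in the earlier methylmalonic acidemia study (Protocol Section 14.1.2), but all three completed it and no event led to discontinuation. This stands: the bias is conditional.

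**The denominator is not stated.** A reader might assume that the plan divides by responders. SAP Section 10.3 names the Evaluable Population, which can contain a boy with no palatability answer. This stands too. It adds a gap of its own, since the SAP never says which denominator the percentages use.

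**Other outputs would show such a boy.** Protocol Section 11.4 has non-completers described separately, with reasons. SAP Section 5 requires tables to show how many subjects the data cover and to separate assessments not performed from missing ones. SAP Section 6 tabulates termination reasons, Section 9 lists sachet counts and Section 12.1.3.6 tabulates adverse events leading to discontinuation. This stands in part. These outputs would alert a careful reader, but none supplies the boy's answers or feeds Table 14.2.3.

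**The illustration is a worst case.** Only the third item concerns refusal or throwing up, and a boy who vomits need not dislike the taste. Nor do the Visit 3 percentages describe only boys who tolerated the drug well: the third item asks about occasional problems, so it also picks up difficulty among boys who continue. Both remarks stand. They limit the size of the effect but do not close the gap in the schedule.

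**Conclusion.** The schedule gap is certain; its effect is not. As planned, a boy who stops before Visit 3 through refusal or vomiting gives no palatability answer, and the unfavourable share could then be understated. With one such boy, two unfavourable responders and the stopper counted as unfavourable, the reported figure is 18% or 17% against 25%. These counts are assumptions, and the effect is zero if no boy stops this early for this reason.

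The point is minor. Palatability is a descriptive secondary endpoint, and the plan makes no test or safety conclusion depend on it. The change is worth making because it costs little and removes a form of missingness that the plan as written would leave in place.

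**What to change.** - **Protocol Table 2 and Section 8.2.12 (and the matching schedule in SAP Section 16):** have the three-question form completed at the ET visit when that visit falls before Visit 3.
- **SAP Section 10.3 and Table 14.2.3:** summarise the Visit 3 response, or the ET response if earlier, with a footnote that ET answers reflect a shorter exposure.
- **SAP Section 10.3:** state whether percentages use responders or the Evaluable N, and show both counts.
- **Table 14.2.3:** show beside the responses the number of treated boys who stopped ataluren before Visit 3 because of refusal or vomiting, out of all treated boys.

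The cost is three questions at a visit that is already required, one table row and one footnote. The downside is a slight mix of exposure times in the summary. The denominator statement and the extra row need only a SAP change, so they are worth making even if the protocol is not amended. No dose or clinical rule is affected.

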8.2.13. Ataluren Administration

Refer to [Section 6.2](#). The clinic staff will administer the first dose of the study drug at Day 1 (Visit 2).

8.2.14. Adverse Events

Systemic AEs must be assessed and documented at each scheduled clinic visit, beginning at Day 1. Additional tests and other evaluations required to establish the significance or etiology of an abnormal result, or to monitor the course of an AE should be obtained when clinically indicated. Patients must be followed for AEs for at least 28 days after the last dose of ataluren administration, or until any drug-related AEs and/or ongoing SAEs have resolved or become stable, whichever is later.

